#### 3.2 ACURATE Prime XL Nested Registry Statistical Assessment

The statistical assessment for the ACURATE *Prime* XL Nested Registry is summarized in the sections below.

3.2.1 Statistical Hypothesis - ACURATE Prime XL Nested Registry

The statistical hypothesis is that the mean aortic valve pressure gradient at 30 days post implant procedure is less than a performance goal (PG):

H0: Gradient30D  $\ge$  PG

H1: Gradient30D < PG

where Gradient30D is the 30-day mean aortic valve pressure gradient for the ACURATE *Prime* XL valve and PG is 15 mmHg.

A one-sample *t*-test will be used to test the one-sided hypothesis at a significance level of 2.5%.

3.2.2 Sample Size Parameters for the ACURATE Prime XL Nested Registry

The sample size calculation is based on the following assumptions.

- Expected 30-day mean pressure gradient from ACURATE Prime XL = 10 mmHg
- Expected standard deviation = 7 mmHg
- PG = 15 mmHg
- Test significance level ( $\alpha$ ) = 0.025 (1-sided)
- Power > 90%
- Evaluable number of subjects = Minimum of 40 subjects
- Expected rate of attrition = 20% (8 subjects)
- Planned enrollment of 50 subjects
- The analysis population for the hypothesis testing will be the subject population implanted with the ACURATE *Prime* XL valve.

*Note:* The expected mean gradient is based on Boston Scientific data on file and published data for large-annulus CoreValve devices (referenced in the protocol synopsis).

### 3.2.3 Success Criteria for the ACURATE Prime XL Nested Registry

If the *P* value from the one-sample *t*-test is < 0.025, the ACURATE *Prime* XL valve will be concluded to have a 30-day mean aortic valve pressure gradient < 15 mmHg. This corresponds to the one-sided upper 2.5% confidence bound of the observed 30-day mean aortic valve pressure gradient being < 15 mmHg.

## 3.3 Quality of Life (QoL) Endpoint

The quality-of-life endpoint is defined as the percentage of subjects who had moderate or greater improvement of Kansas City Cardiomyopathy Questionnaire Overall Summary Score (KCCQ-OSS) from baseline to 1-year follow-up for subjects who are implanted with the ACURATE valve.

Moderate or greater improvement is defined as more than 10 points improvement of KCCQ-OSS, where the improvement is calculated as KCCQ-OSS at 1-year minus KCCQ-OSS at baseline.

*Note:* Subjects who died within 1 year and/or had KCCQ-OSS at both baseline and 1-year follow-up will be included in the QoL Endpoint analysis. If a subject died without KCCQ-OSS at 1-year, this subject is considered as not having a moderate or greater improvement of KCCQ-OSS.

### 3.3.1 Statistical Hypothesis

Percentage of subjects with moderate or greater improvement of KCCQ-OSS from baseline to 1-year follow-up meets the performance goal (PG):

H0:  $P_{moderate_improve} \le PG$ 

 $H_1: P_{moderate_improve} > PG$ 

where  $P_{moderate\_improve}$  is the percentage of subjects with moderate or greater improvement of KCCQ-OSS from baseline to 1-year follow-up. PG is set to be 50%.

### 3.3.2 Statistical Test Method

A one-sample z-test will be used to test the one-sided hypothesis at a significance level of 2.5%.

### 3.3.3 Power and Sample Size

The sample size calculation is based on the following assumptions.

- Performance Goal (PG) = 50%
- Expected Rate = 55%
- Test significance level (a) = 0.025 (1-sided)
- Number of subjects to be enrolled > 980
- Expected attrition rate = 20% (196 subjects)

- Number of evaluable subjects > 784
- Power > 80%

**Note**: Analysis population includes subjects who are implanted with ACURATE valve in the ACURATE IDE Main Randomized Cohort (750 subjects), ACURATE *Prime* XL Nested Registry (50 subjects), Continued Access Study (maximum of 1,000 subjects) and ACURATE Extended Durability Study (approximately 50 subjects).

**Note**: The moderate or greater improvement was noted in 55% of the subjects with the 95% CI [52.0%, 58.2%] from the meta-analysis random effect model using data from the trials/cohorts listed below. Considering margin of errors and variabilities of the observed data across different studies and operative risks, a 5% margin is applied to the historical rate of 55% to derive the PG. Thus the 50% PG (55% minus 5%) is proposed for a clinical meaningful moderate improvement of the KCCQ-OSS for this study. **Note**: Trials/cohorts data included in the meta-analysis:

Boston Scientific REPRISE III study - High/Extreme (CoreValve), CoreValve US Pivotal Extreme Risk Trial (TAVR), PARTNER Trial High Risk (TAVR), PARTNER 2 RCT (TF) - Intermediate (TAVR), PARTNER 3 Low Risk (TAVR).

### 3.3.4 Success Criteria

If the *P* value from the one-sample z-test is < 0.025, it concludes that the QoL Endpoint for the study meets the pre-specified PG of 50%. This corresponds to the one-sided lower 2.5% confidence bound of the observed percentage of subjects with moderate or greater improvement of KCCQ-OSS from baseline to 1-year follow-up is > 50%.

# 3.3.5 QoL Analysis

The QoL endpoint analysis set will be based on subjects who are implanted with the ACURATE valve from ACURATE valve in the ACURATE IDE Main Randomized Cohort, ACURATE *Prime* XL Nested Registry, Continued Access Study, and ACURATE Extended Durability Study.

The analysis set will include subjects who died prior to the 1-year visit (within 365 days post index procedure) or have both baseline and 1-year KCCQ-OSS.

**Note**: If a subject died within 365 days post index procedure without KCCQ-OSS at 1year, this subject is considered as not having a moderate or greater improvement of KCCQ-OSS.

This planned analysis will be performed after the subjects completed 1-year follow-up. Other QoL/KCCQ data may be analyzed using the same analysis set as appropriate.

# 3.4 Other Endpoints

Additional analyses at interim for other CEC endpoints will be performed on all enrolled Main Randomized Cohort subjects (N=1500) using the piecewise exponential prediction models specified in Section 3.1.5. Event rates and credible intervals will be provided.

For the Main Randomized Cohort (including 4D-CT Cohort subjects), the 4D-CT Cohort, and the Extended Durability Study, the analysis will be conducted separately. Statistical comparisons for these endpoints will be made between the test and the control arms within each cohort. 4D-CT analysis will include the data for subjects who are eligible for the Main Randomized Cohort analysis at the time of the interim analysis. Analyses for other endpoints will use the standard frequentist methods (details in Section 4.1), such as Chi-square or Fisher's exact for binary variables, T-test for continuous variables, or Log-rank test for time-to-event or Kaplan–Meier survival analysis when they are appropriate, at both the interim and the final analyses. Additional analysis methods may be used when they are appropriated (e.g. Breslow-day test for interaction, ANOVA test or Kruskal-Wallis test for continuous variables, one-sample T-test or McNemar's test for paired analysis).

For the roll-in, the ACURATE *Prime* XL Nested Registry, and the Continued Access Study cohorts, the analyses will be conducted separately, and descriptive analyses will be provided.

Reference:

FDA Guidance for Industry and FDA Staff: Guidance for the Use of Bayesian Statistics in Medical Device Clinical Trials, February 2010

# 4 GENERAL STATISTICAL METHODS

### 4.1 General Methods

Descriptive statistics and statistical comparisons will be presented on the trial results by treatment group for the Main Randomized Cohort subjects (including 4D-CT Cohort subjects), 4D-CT Cohort, and the Extended Durability Study. Descriptive statistics will be presented separately for roll-in subjects, the ACURATE *Prime* XL Nested Registry subjects, and the Continued Access Study subjects. For continuous variables, summaries will include the sample size (N), mean, standard deviation, minimum, and maximum. Frequency tables will be used to summarize discrete variables. The difference between

comparison groups and its 95% confidence intervals will be calculated. Treatment groups will be compared for randomized subjects using the chi-square test or Fisher's exact test for binary variables and Student's t-test for continuous variables. The appropriate t-test (Pooled or Scatterthwaite methods) will be used based on the test of equality of variances (Levene's test or F-test) between the treatment groups. The chi-square test is used by default; the Fisher Exact test is used in place of the chi-square test when one or both of the following occur: total number of samples  $\leq$ 40 and/or at least one cell count in the 2X2 table has expected value less than 5. Additional tests such as: log-rank test for Kaplan-Meier rate or chi-square test for 2xn table may be used when they are appropriate. Additional analysis methods may be used when they are appropriated (e.g. Breslow-day test for interaction, ANOVA test or Kruskal-Wallis test for continuous variables, one-sample T-test or McNemar's test for paired analysis).

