- k: A CT angiogram of the aortic complex must be performed within 180 days prior to CRC approval (and should be performed within 90 days if possible) to evaluate the aortic valve anatomy and aortic root dimensions for device sizing. CT angiogram must be performed according to the CT/Angiography Core Laboratory procedure guidelines (see study Manual of Operations). It must be sent to the core laboratory for detailed measurements and analyses in advance of the CRC review where results will be assessed to confirm subject's eligibility.
- 1: An assessment of the iliofemoral system must be performed within 180 days prior to CRC approval (and should be performed within 90 days if possible). A CT angiogram of the iliofemoral system should be performed for complete visualization of the iliac and femoral arteries to assess for dimensions, tortuosity, and calcification. The CT angiogram should be performed per the procedure guidelines (see study Manual of Operations) and sent to the CT core laboratory with the screening CT angiogram of the aortic structure. An iliofemoral invasive angiogram may be substituted for the iliofemoral CT angiogram.
- m: Includes the Kansas City Cardiomyopathy and SF-12 QOL questionnaires. Baseline QOLs must be performed within 30 days prior to the index procedure.
- n: QOL survey at 5 years.
- o: Procedural cine-angiogram including the baseline images of the aortic complex and the final post-deployment aortogram of the ascending aorta must be performed and sent to the CT/Angiography core laboratory for analysis.
- p: Balloon aortic valvuloplasty following standard techniques must be performed with an appropriately sized valvuloplasty balloon before test device implantation; BAV may be performed before control device implantation, but planned use should be reviewed by the CRC.
- q: In subjects who receive a study device, AEs and ADEs will be monitored and collected from the time of enrollment through 12-month follow-up. For subjects who do not receive a study device, AEs will be monitored through 12-month follow-up.

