11.1.4. Post-procedure Measurements

Post-procedure information will be collected at regularly scheduled follow-up examinations as detailed in the clinical study schedule (Table 10.1-1) and will be summarized using descriptive statistics for continuous variables (e.g., mean, standard deviation, n, minimum, maximum) and frequency tables or proportions for discrete variables. Estimates will be reported by treatment group and, for randomized subjects (Main Randomized Cohort and Extended Durability Study), differences between treatment groups and their 95% confidence intervals will be presented. Treatments for the randomized subjects will be compared with the chi-square or Fisher exact test for discrete variables and the Student t-test for continuous variables. No inferences are planned on the additional measurements and, therefore, alphaadjustments for multiple comparisons will not be used. The Kaplan-Meier product-limit method will be used to estimate rates for time-to-event endpoints and treatment groups will be compared using the Log-rank and Wilcoxon tests. Adverse event and SAE rates will be reported. No formal statistical testing will be done for the Roll-In, Extended Durability Study, or ACURATE CAS subjects. Please see Section 11.1.1.1 and Section 11.1.2, respectively, regarding statistical testing for the Main Randomized Cohort and the ACURATE Prime XL Nested Registry.

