#### 5.2 Other Clinical Assessments

The following assessment will be evaluated.

• Device performance endpoints peri- and post-procedure:

- Successful vascular access, delivery and deployment of the study valve and successful retrieval of the delivery system
- Grade of aortic valve regurgitation: paravalvular, central and combined
- Device success, defined as absence of procedural mortality, correct positioning of a single transcatheter valve in the proper anatomical location, and intended performance of the study device (indexed effective orifice area [iEOA]
   >0.85 cm^2/m^2 for BMI <30 kg/cm^2 and iEOA >0.70 cm^2/m^2 for BMI ≥30 kg/cm^2 plus either a mean aortic valve gradient <20 mm Hg or a peak velocity < 3m/sec, and no moderate or severe prosthetic valve aortic regurgitation)

- Additional indications of prosthetic aortic valve performance as measured by transthoracic echocardiography and assessed by an independent core laboratory, including EOA, mean and peak aortic gradients, peak aortic velocity, and grade of aortic regurgitation
- Functional status as evaluated by New York Heart Association (NYHA) classification
- Neurological status as determined by the following:
  - National Institutes of Health Stroke Scale (NIHSS) conducted by a neurology professional or certified personnel at discharge and 1 year
  - Modified Rankin Scale (mRS) conducted by a neurology professional or certified personnel at discharge and all follow-up visits
  - Neurological physical exam conducted by a neurologist, neurology fellow, neurology physician assistant, or neurology nurse practitioner in all subjects where stroke is suspected

Health status as evaluated by Kansas City Cardiomyopathy and SF-12 Quality of Life (QOL) questionnaires at baseline, 1 month, 1 year, and 5 years.

For subjects in the CT Imaging Substudy, assessments using 4D CT at 30 days and 1 year will be done as listed below. Data will be evaluated by an independent CT core laboratory.

- Assessment of leaflet mobility
- Assessment of hypoattenuated leaflet thickening (HALT)
- Assessment of leaflet thrombosis

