#### 5.7 Other Analyses

The general statistical methods (see Section 4.1) will be applied appropriately for the following analyses. The ITT and implanted analysis sets (see Section 4.2) will be used for following analyses.

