#### 5.7.7 Other Clinical Assessment at various points

- NYHA classification
- 12-lead electrocardiogram (ECG)
- Risk assessments: Society of Thoracic Surgeons (STS) score, euroSCORE II
- Frailty, disability, and comorbidity assessments
- A CT angiogram
- NIH Stroke Scale (NIHSS)
- Modified Rankin Scale (mRS) score
- Quality of Life (QOL)
- SF-12 QOL Questionnaires
- 4D CT at 30 days and 1 year

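### Randomized comparisons of KCCQ and SF-12 scores rest on an unadjusted t-test, although a baseline score is required; adjusting for it would give tighter intervals at no data cost

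*SAP*

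**What the plan says.** SAP 5.2 lists "Health status as evaluated by Kansas City Cardiomyopathy and SF-12 Quality of Life (QOL) questionnaires at baseline, 1 month, 1 year, and 5 years". The data collection schedule in Protocol 10.1 makes the first of these compulsory: "Baseline QOLs must be performed within 30 days prior to the index procedure".

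For the analysis, SAP 3.4 says of the other endpoints that "Statistical comparisons for these endpoints will be made between the test and the control arms within each cohort". The method comes from SAP 4.1, which compares the randomized arms "using the chi-square test or Fisher's exact test for binary variables and Student's t-test for continuous variables", with the pooled or unequal-variance form chosen by a test of variances. SAP 5.7 extends this to its own list: "The general statistical methods (see Section 4.1) will be applied appropriately for the following analyses". That list, in SAP 5.7.7, names quality of life and "SF-12 QOL Questionnaires". Protocol 11.1.4 agrees: treatments for the randomized subjects "will be compared with the chi-square or Fisher exact test for discrete variables and the Student t-test for continuous variables". It adds that group differences will carry 95% confidence intervals and that no inference is planned on the additional measurements.

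Three other provisions bear on the point:

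- SAP 3.4 and 4.1 allow further methods where suitable. The examples are Breslow-Day, ANOVA, Kruskal-Wallis, one-sample t and McNemar.
- SAP 5.6 plans univariate and stepwise logistic models for the primary and additional endpoints. Their covariate list includes treatment group and operative risk, but no baseline KCCQ or SF-12 score.
- SAP 3.3 tests the share of ACURATE-implanted subjects whose KCCQ overall summary score rises by more than 10 points at 1 year, against a 50% performance goal. It has no control arm.

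**The concern.** The between-arm contrast in mean health status has one named method, and that method makes no explicit use of the most informative covariate for a follow-up score, the same score at baseline. The outcome scale is also open. A t-test on follow-up scores ignores baseline. A t-test on change subtracts all of it, which over-corrects whenever the correlation is below 1. Given the baseline imbalance that chance happens to produce, the first leaves part of it in the estimate and the second reverses part of it. Analysis of covariance estimates the same mean difference and is at least as precise as either in large samples.

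At stake is the width of the reported intervals for KCCQ and SF-12 differences, which Protocol section 12 says may also feed a health-economics analysis. Leaving the scale unstated also leaves a choice to the analyst after the data are in, in a trial the protocol describes as unblinded.

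**Working it through.** **Is there a plan figure to reproduce?** None exists for the randomized KCCQ or SF-12 comparison. The nearest is SAP 3.3.3, for the single-arm test: goal 0.50, expected 0.55, one-sided 0.025, 784 evaluable subjects, power above 80%.

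- Power = Φ[(0.05 − 1.960·√(0.25/784)) / √(0.2475/784)] = Φ[(0.05 − 0.0350)/0.01777] = 80.07%.
- Enrollment: 784/(1 − 0.20) = 980, of which 20% is 196.

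Both agree with the SAP. This test has no comparator, so it is not affected by what follows.

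**Inputs for the randomized comparison.** 750 subjects per arm (SAP 3.1.2). The correlation ρ between baseline and follow-up score is in neither document and is assumed to be 0.3 to 0.6. The score variance σ² is assumed equal at baseline and follow-up.

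**Large-sample variance of the treatment difference, n per arm:**

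- t-test on follow-up scores: 2σ²/n
- t-test on change scores: (2σ²/n)·2(1 − ρ)
- analysis of covariance on baseline: (2σ²/n)·(1 − ρ²)

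The variance ratio of analysis of covariance to the follow-up t-test is therefore 1 − ρ². Its ratio to the change-score t-test is (1 − ρ²)/[2(1 − ρ)] = (1 + ρ)/2. The reduction in standard error is 1 minus the square root of the ratio.

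| ρ (assumed) | Variance ratio vs follow-up | SE reduction | Variance ratio vs change | SE reduction |
|---|---|---|---|---|
| 0.3 | 0.91 | 4.6% | 0.65 | 19.4% |
| 0.4 | 0.84 | 8.3% | 0.70 | 16.3% |
| 0.5 | 0.75 | 13.4% | 0.75 | 13.4% |
| 0.6 | 0.64 | 20.0% | 0.80 | 10.6% |

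Below the assumed range, at ρ = 0.2, the gain over a follow-up t-test is only 2.0%, while the gain over a change-score t-test is 22.5%. The two gains move in opposite directions, which is why the unstated outcome scale matters.

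**In score units.** Take 600 per arm, which is 750 less the 20% attrition that SAP 3.3.3 uses for KCCQ; applying it to both arms is an assumption. The difference detectable with 80% power at two-sided 0.05 is (1.960 + 0.842)·√(2/600) = 0.162 SD for follow-up scores. Multiply by √[2(1 − ρ)] for change scores and by √(1 − ρ²) for analysis of covariance.

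| ρ (assumed) | Follow-up t-test | Change t-test | Analysis of covariance |
|---|---|---|---|
| 0.3 | 0.162 | 0.191 | 0.154 |
| 0.4 | 0.162 | 0.177 | 0.148 |
| 0.5 | 0.162 | 0.162 | 0.140 |
| 0.6 | 0.162 | 0.145 | 0.129 |

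These figures cover the baseline score only. Any further gain from operative risk or intended control device is not included.

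**The case against.** The strongest reply is that nothing depends on these comparisons. Protocol 11.1.4 plans no inference on them, Protocol 11.3.1 places them outside the statistical hypotheses, and no power or success criterion is attached. With 1:1 randomization and 750 per arm, both t-tests are unbiased and chance imbalance should be small. All of this stands, and it limits the point to one of efficiency.

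A second reply is that the clause on additional methods is open-ended, so analysis of covariance is already permitted. It is permitted, but not pre-specified, and none of the examples given adjusts for baseline.

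A third is that SAP 5.6 already brings in operative risk for additional endpoints. A reader might infer that nothing in the plan adjusts for risk, and that would be wrong. But those models are logistic, select predictors stepwise and omit the baseline scores, so they do not supply an adjusted mean difference in KCCQ or SF-12.

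A fourth concerns the remedy. A complete-case covariate model would drop subjects who have a follow-up score but no baseline, whom a t-test on follow-up scores would keep. That is fair, and the fix has to deal with it.

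**Conclusion.** The point holds as a modest, free improvement. The plan names an unadjusted t-test, leaves its scale open, and does not adjust these scores for a baseline that it requires. Over an assumed correlation of 0.3 to 0.6, the standard error would fall by about 5-20% against follow-up scores and about 11-19% against change scores. That range depends on the assumed correlation and on equal variances at the two times.

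Three stronger readings are tempting, and the documents do not support them:

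- **That every subject has a baseline score.** It is required, not guaranteed. SAP 3.3 includes survivors only if both scores are present, and a randomized subject with no index procedure may have none.
- **That the trial gives up the equivalent of 500 subjects.** The sum 1,500/0.75 = 2,000 needs a correlation of exactly 0.5 and complete pairs in all 1,500. Neither is in the documents.
- **That the trial's conclusions are biased or weakened.** The loss is precision in descriptive intervals. The primary endpoint and the KCCQ performance-goal test do not use this comparison.

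**What to change.** In SAP 4.1 and Protocol 11.1.4, state that between-arm comparisons of KCCQ and SF-12 at each visit use analysis of covariance, or a repeated-measures model, with treatment, baseline score, operative-risk stratum and intended control device. Report the adjusted mean difference with its 95% interval. Add three rules:

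- **Missing baseline.** Keep these subjects in the analysis, for example by imputing the baseline mean or by a repeated-measures model that constrains the baseline means to be equal across arms.
- **Deaths.** Say how they enter. SAP 3.3 counts a death without a 1-year score as no improvement, but that rule does not carry over to a mean score.
- **Timing of baseline.** Use a score taken before randomization, or say how later ones are handled. The questionnaire window is tied to the procedure, and Protocol 7.2 allows up to 14 days between randomization and treatment, so a baseline can be completed after allocation.

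The cost is wording and some programming, with no new data. SAP 5.8 already provides for such a change through an amended SAP approved before the analysis is run.

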10.10.5. Follow-up (±60 Days) at 7 and 10 Years

All implanted subjects must be evaluated in person or via telehealth at 7 and 10 years after the index procedure, with a window of ± 60 days. The following assessments must be completed. The ACURATE IDE eCRFs identify the specific data points to be collected.

- NYHA classification
- Current antiplatelet, anticoagulant (if applicable)
- TTE, including assessment of effective orifice area, peak and mean aortic valve gradient pressure, aortic regurgitation assessment, peak aortic velocity, and LVEF per the Echocardiography Core Laboratory procedure guidelines. All TTEs must be forwarded to the core laboratory for independent analyses.

Note 1: TTE must be done for all subjects who have a transcatheter valve implanted in the aortic position during the index procedure, even if the associated follow-up assessment is carried out via telehealth.

• Serious adverse event (SAE, SADE, UADE, and relevant VARC events to be adjudicated by the CEC) assessment for test and control devices and device deficiencies assessment for test device(s) with associated treatment.

Note 2: Relevant VARC events to be adjudicated by the CEC include the following: mortality, stroke, spontaneous myocardial infarction, acute kidney injury, repeat procedure for valve-related dysfunction, hospitalization for valve-related symptoms or worsening congestive heart failure (NYHA III or IV), new pacemaker, new onset atrial fibrillation or atrial flutter, prosthetic aortic valve malpositioning (valve migration, valve embolization, or ectopic valve deployment), TAV-in-TAV, prosthetic aortic valve thrombosis and endocarditis.

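### The SAP gives no rule for deaths in the randomized KCCQ and SF-12 comparisons, so by default they describe survivors with a score, while SAP 3.3 counts death as no improvement in ACURATE subjects only

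*SAP*

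**What the plan says.** SAP 3.4 covers the endpoints other than the primary one. For the Main Randomized Cohort, the 4D-CT cohort and the Extended Durability Study it states: "Statistical comparisons for these endpoints will be made between the test and the control arms within each cohort". It refers to SAP 4.1 for the methods, which are a chi-square or Fisher test "for binary variables and Student's t-test for continuous variables", with the difference between groups and its 95% confidence interval. SAP 5.2 lists the KCCQ and SF-12 "questionnaires at baseline, 1 month, 1 year, and 5 years", and SAP 5.7.7 lists quality of life again. None of these sections gives a dead subject a value, a rank or a category.

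SAP 3.3 is different. Its endpoint is the percentage of ACURATE-implanted subjects whose KCCQ overall summary score rises by more than 10 points from baseline to 1 year. If a subject dies without a 1-year score, "this subject is considered as not having a moderate or greater improvement of KCCQ-OSS". SAP 3.3.5 sets the matching inclusion rule: the subject either died within 365 days of the procedure or has both scores. The test is single-arm, against a 50% performance goal, and pools four cohorts. SAP 3.3.5 also lets other KCCQ data use the same analysis set, but that set contains no control subjects.

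**The concern.** A subject without a score cannot enter a mean or a t-test. Followed as written, the plan compares ACURATE survivors who have a score with Control survivors who have a score. The same KCCQ data in ACURATE subjects are then analysed a second time under SAP 3.3, where deaths count as failures. The two results answer different questions, and only the first has a randomized comparator.

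What is missing is a randomized comparison of the proportion alive and improved. If one arm loses more patients and the survivors of both arms do equally well, the planned KCCQ comparison shows no difference although fewer patients in that arm are alive and better. Deaths accumulate, so the gap matters more at 5 years, the last planned KCCQ. The SAP 3.3 rule stops at 1 year.

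**Working it through.** **The plan's own figure.** SAP 3.3.3 states power above 80% for a 50% goal, a 55% expected rate, one-sided 0.025 and 784 evaluable subjects.

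- Power = Φ[(√784 × 0.05 − 1.96 × 0.5) / √(0.55 × 0.45)] = Φ[(1.40 − 0.98) / 0.497] = 80.1%. The exact binomial gives 80.0%.
- Attrition: 784 / (1 − 0.20) = 980, so 196 are lost.

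The figure reproduces. The SAP states no figure for the randomized quality-of-life comparison, so the rest is illustration.

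**Inputs for the illustration**

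- Risk mix (SAP 3.1.2): 10% extreme, 25% high, 30% intermediate, 35% low.
- 1-year mortality in the CoreValve studies (Protocol Table 4.1-1): 24.3% extreme, 14.2% high, 6.7% intermediate, 2.4% low. The table's symbols group high and extreme risk together; the split here follows the study names.
- Evaluable subjects (SAP 3.1.2): 712 per arm.
- Responder rate with death counted as failure: 55%, the rate SAP 3.3.3 expects for an endpoint defined that way.

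**Step 1: mortality and survivor response.** Weighted 1-year mortality is 0.10 × 24.3 + 0.25 × 14.2 + 0.30 × 6.7 + 0.35 × 2.4 = 8.8%. The responder rate among survivors is s = 0.55 / (1 − 0.088) = 60.3%.

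**Step 2: the two comparisons.** Assume s is the same in both arms, and let m be mortality.

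- Survivors only: s − s = 0, whatever the mortality.
- Death as not improved: s(1 − m_T) − s(1 − m_C) = −s(m_T − m_C).

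| Time | Control mortality | Assumed excess in ACURATE arm | Survivors-only difference | Death as not improved | z, 712 per arm |
|---|---|---|---|---|---|
| 1 year | 8.8% | 2 points | 0.0 | −1.2 | −0.5 |
| 1 year | 8.8% | 3 points | 0.0 | −1.8 | −0.7 |
| 1 year | 8.8% | 5 points | 0.0 | −3.0 | −1.1 |
| 5 years | 25–50% (assumed) | 5 points | 0.0 | −3.0 | about −1.2 |
| 5 years | 25–50% (assumed) | 10 points | 0.0 | −6.0 | −2.3 to −2.6 |

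The difference is s times the excess mortality, so control mortality enters only through s. The 5-year rows also assume that s stays at 60.3%.

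**Step 3: the mean score.** Assume the underlying KCCQ change has mean 15 and SD 20 in both arms, with a correlation of 0 to 0.6 between score and survival. The survivors-only mean then favours the arm with more deaths by 0 to 0.6 points at 8.8% versus 11.8% mortality, and by 0 to 1.8 points at 35% versus 45%. With zero correlation there is no such shift.

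**The case against.** The strongest case on the other side has five parts.

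- **The SAP does not say survivors only.** This stands. SAP 4.2 puts additional measurements on ITT and implanted sets, and SAP 3.1.7, in the primary-endpoint section, leaves missing data to the nature of the outcome. Neither says what a dead subject contributes, so survivors with a score is the default consequence of a t-test, not a stated rule.
- **Mortality is not hidden.** This stands. A reader might infer that the plan could conceal a mortality difference. It could not: all-cause death is part of the primary endpoint, and SAP 5.1 gives Kaplan-Meier rates from 30 days to 10 years. The gap lies inside the quality-of-life results.
- **No decision rests on these comparisons.** This stands. Protocol 11.1.4 plans no inference on additional measurements. It does still prescribe tests and 95% confidence intervals by randomized arm, and Protocol Section 12 allows quality of life to feed a health-economics analysis.
- **SAP 3.3 serves another purpose.** This stands in part. The SAP revision history ties it to a national coverage determination, so it is no admission that the t-test is wrong, and a summary among survivors shown beside mortality is legitimate. It does show that the sponsor has an accepted responder definition that includes death and could be applied to both arms.
- **The 1-year effect is small.** This stands. In the illustration z is at most about 1.1 in size.

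Two further readings are tempting. One is to set the step from 55% to 60.3% against the 5-point gap between goal and expected rate. That step is a shift in level within one arm and largely cancels between arms. The other is to extend the point to NYHA class. NYHA is categorical and outside the t-test text; SAP 4.1 says only that a "chi-square test for 2xn table may be used when they are appropriate". It is also collected at 7 and 10 years. The point is therefore confined to KCCQ and SF-12.

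**Conclusion.** The concern holds as a gap in pre-specification. The SAP is silent on deaths in the randomized KCCQ and SF-12 comparisons, its default methods give a result among survivors with data, and its one rule that counts deaths has no control arm and ends at 1 year. A between-arm difference in patients alive and improved would not appear in any planned quality-of-life comparison.

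The unseen responder difference is about 1 to 3 points at 1 year for excess mortality of 2 to 5 points, and about 3 to 6 points at 5 years for excess mortality of 5 to 10 points. The excess mortality, all 5-year mortality and the equal survivor response are assumptions; the documents supply none of them. A reader might infer that the survivors-only result always flatters the arm with more deaths. That needs a correlation between score and survival, which the documents do not give. The primary endpoint and the SAP 3.3 test are unaffected. This is a worthwhile, inexpensive improvement to supportive analyses.

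**What to change.** Add to SAP 3.4, for the Main Randomized Cohort, a comparison of ACURATE with Control at 1 year and at 5 years:

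- **Outcome:** the SAP 3.3 responder definition, a KCCQ overall summary score improvement of more than 10 points. Death before the visit without a score counts as not improved.
- **Inclusion:** the SAP 3.3.5 rule in both arms, meaning the subject died before the visit or has both the baseline and the visit score.
- **Reporting:** the difference between arms with its 95% CI.
- **Accounting by arm:** numbers dead, not implanted or explanted, and otherwise missing. Protocol 10.1 requires no quality-of-life assessment in subjects without a study valve or after surgical explant, so their scores are absent for reasons other than death.

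Keep the KCCQ and SF-12 t-tests and label them 'among survivors with data'.

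The cost is SAP wording and one or two tables from data already collected. The downside is an endpoint that combines death with health status, which SAP 3.3 already accepts. Living subjects without a score still drop out while deaths stay in, which is why the accounting by arm is needed. The change should be made before the unblinding at the formal interim analysis (SAP 4.3), so that the handling of death is not chosen after the results are seen.
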